### Week 0 day 2 (W0D2)

To be performed 24 hours ±6 hours after the administration visit at W0. The following evaluations and sampling are to be performed.

- Concomitant illness/Concomitant medication
- Vital signs
- Adverse events
- o Hematology: RBC, WBC with differential count, platelets, hemoglobin; MCV, hematocrit
- o Biochemistry: sodium, potassium, chloride, bicarbonate, calcium, magnesium, phosphate, total proteins, and albumin, urea, uric acid, creatinine, calculated creatinine clearance, ALP, total bilirubin, LDH, AST (SGOT), ALT (SGPT), gamma glutamyl transferase (GGT), amylase, lipase, glucose, C-reactive protein (CRP) and fibrinogen
- 0 PK 0

MOD-3783

Release date: Edition number

MOD-3783

12 August 2016

GED version

# Week 0 day 8 (W0D8)

W0D8 visit will be performed 7 days ±3 days after IPH2201 administration. The following assessments should be performed:

- Concomitant illness/Concomitant medication
- o Vital signs
- o Adverse events
- o Hematology
- Biochemistry
- o PK

### 6.2.1.2 Cycle 2

Cycle 2 is a 2-week cycle and consists of 2 visits, the dosing visit (W2) and a visit 24 hours after dosing (W2D2).

### Week 2 day 1 (W2)

As for cycle 1, IPH2201 only will be administered at week 2 day 1 (W2) visit.

The following pre-dose assessments must be done prior to IPH2201 administration:

- Concomitant illness/Concomitant medication
- Safety assessments
  - o Vital signs (including weight)
  - o Physical examination, focused on symptoms and new findings (from screening visit)
  - ECOG status
  - o Adverse events
- Pre-dose Safety laboratory (H0)
  - Biochemistry: sodium, potassium, chloride, bicarbonate, calcium, magnesium, phosphate, total proteins, and albumin, urea, uric acid, creatinine, calculated creatinine clearance, ALP, total bilirubin, LDH, AST (SGOT), ALT (SGPT), gamma glutamyl transferase (GGT), amylase, lipase, glucose, C-reactive protein (CRP) and fibrinogen
  - o Hematology: RBC, WBC with differential count, platelets, hemoglobin; MCV, hematocrit
- PK assessment at H0

IPH2201 administration should be performed 14 days +/- 3 days after the previous administration.

Redosing criteria include the resolution of any grade 3 or higher adverse event to grade 2 or lower, the absence of disease progression and the absence of grade 4 treatment-related non-hematologic AE following the previous administration.

- The following post-dose assessments are required at W2 visit:
  - Biochemistry at H0+4: sodium, potassium, chloride, bicarbonate, calcium, magnesium, phosphate, total proteins, and albumin, urea, uric acid, creatinine, calculated creatinine clearance, ALP, total bilirubin, LDH, AST (SGOT), ALT (SGPT), gamma glutamyl transferase (GGT), amylase, lipase, glucose, C-reactive protein (CRP) and fibrinogen
  - Hematology at H0+4: RBC, WBC with differential count, platelets, hemoglobin; MCV, hematocrit
  - PK assessments at H0+1 (end of IPH2201 infusion) and H0+3 (2 hours after end of IPH2201 infusion)

Release date: Edition number

MOD-3783

12 August 2016

**GED** version

# Week 2 day 2 (W2D2)

To be performed 24 hours +/- 6 hours after the administration visit at W2. All the following evaluations and sampling are to be performed.

- o Concomitant illness/Concomitant medication
- o Vital signs
- o Adverse events
- o Hematology
- o Biochemistry

### 6.2.1.3 Cycle 3

Cycle 3 is a 2-week cycle and consists of 3 visits, the dosing visit (W4), a visit 24 hours after dosing (W4D2) and a visit 1 week after dosing (W4D8).

#### Week 4 day 1 (W4)

During phase 1b part patients will receive both IPH2201 and ibrutinib at Week 4 (W4) as the first cycle of combined therapy.

The following pre-dose assessments must be done prior to IPH2201 and ibrutinib administrations:

- Concomitant illness/Concomitant medication
  - Safety assessments
    - o Vital signs (including weight)
    - o Physical examination, focused on symptoms and new findings (from screening visit)
    - ECOG status
    - o Adverse events
  - Pre-dose Safety laboratory (H0)
    - o Hematology
    - o Biochemistry
    - o Coagulation factors
    - o Urinalysis
  - Pre-dose PK/PD assessments (H0)
    - PK
      <
  - Other specific assessments at cycle 3 are required, after completion of the treatment period by IPH2201 alone:
    - Tumor assessment: A tumor assessment by physical examination and a new CT-scan are required at W4 visit
    - A bone marrow examination: optional at cycle 3, and requiring specific consent from the patient

Release date: Edition number

MOD-3783

12 August 2016

**GED** version

IPH2201 administration should be performed 14 days  $\pm$  3 days after previous administration. Redosing criteria include the resolution of any grade 3 or higher adverse event to grade 2 or lower, the absence of disease progression and the absence of grade 4 treatment-related non-hematologic AE following the previous administration.

For patients in dose escalation phase Ib, ibrutinib will be administered at the dose of 420 mg (three 140 mg capsules) orally once daily, from cycle 3 day 1.

IP2201 will be administered first, followed by ibrutinib, to be taken after the end of IPH2201 perfusion.

The following post-dose assessments are required at C3D1:

- o Biochemistry at H0+4
- o Hematology at H0+4
- PK assessments at H0+1 (end of IPH2201 infusion) and H0+3 (2 hours after end of IPH2201 infusion)

### Week 4 day 2 (W4D2)

To be performed 24 hours +/- 6 hours after the administration visit at W4. All the following evaluations and sampling are to be performed.

- o Concomitant illness/Concomitant medication
- o Vital signs
- o Adverse events
- Hematology
- Biochemistry
- o PK

### Week 4 day 8 (W4D8)

W4D8 visit will be performed 7 days  $\pm$  3 days after IPH2201 administration. The following assessments should be performed:

- o Concomitant illness/Concomitant medication
- o Vital signs Adverse events
- o Hematology
- o Biochemistry
- o PK

# 6.2.1.4 Cycle 4

Cycle 4 is a 2-week cycle and consists of 2 visits, a dosing visit (W6) and a visit 24 hours after dosing (W6D2).

### Week 6 day 1 (W6)

The following pre-dose assessments must be done prior to IPH2201 and ibrutinib administrations:

- Concomitant illness / Concomitant medication
- Safety assessments as following:
  - o Vital signs (including weight)

Release date: Edition number 12 August 2016 MOD-3783

**GED** version

- Physical examination, focused on symptoms and new findings (from screening visit)
- ECOG status
- o Adverse events
- Pre-dose Safety laboratory (H0)
  - o Biochemistry
  - o Hematology
  - o A 12-lead ECG
- Pre-dose PK/PD assessments (H0)
  - o PK
  - 0
  - 0

IPH2201 administration should be performed 14 days +/- 3 days after the previous administration.

- The following post-dose assessments are required at W6 visit:
  - Biochemistry at H0+4
  - Hematology at H0+4 PK assessments at H0+1 (at end of the 1-hour infusion of IPH2201)

### Week 6 day 2 (W6D2)

To be performed 24 hours +/- 6 hours after the administration visit at W6. The following evaluations and sampling are to be performed:

- o Concomitant illness/Concomitant medication
- o Vital signs
- o Adverse events
- Hematology
- o Biochemistry

# 6.2.1.5 Cycle 5 to cycle 16

From cycle 5 (W8) cycles last for 4 weeks and consist of 1 dosing visit only.

Patients who were enrolled according to a previous version of the protocol

will switch to a 4-week cycle schedule of

visits after they have completed and signed an amended informed and consent form. The switch to the new schedule of visits will occur in place of the nearest *odd visit*.

The following pre-dose assessments must be done prior to IPH2201 and ibrutinib administrations:

- Concomitant illness/Concomitant medication
- Tumor assessment:
  - a tumor assessment by physical examination is required at all dosing visits starting from W8 visit (monthly assessments);
  - a CT-scan should be performed at W16 and at any other visit to confirm a CR or progression, whenever one of these events is suspected
- Safety assessments
  - Vital signs (including weight)
  - Physical examination, focused on symptoms and new findings (from screening visit)

[figure not shown]
Release date: Edition number

MOD-3783

12 August 2016

GED version

- ECOG status
- o Adverse events
- o A 12-lead ECG is required at W16 and W32
- Pre-dose Safety laboratory (H0)
  - Hematology
  - Biochemistry, required at W8, W12, W16, then every 2 months, at W24, W32, W40 and W48
  - Coagulation factors to be performed at W8
  - o Urinalysis at W32 only
- Pre-dose PK/PD assessments (H0)
  - o Pharmacokinetics at W12, W20, W28, W36, W44, W52

IPH2201 administration should be performed 28 days +/- 7 days after previous administration.

IP2201 will be administered first, followed by ibrutinib taken after the end of IPH2201 perfusion.

The following post-dose assessments are required:

o PK assessments at H0+1 (end of IPH2201 infusion) at W12, W20, W28, W36, W44, W52

# 6.2.2 Patients in part 2 – Phase Ila

### 6.2.2.1 Cycle 1

Cycle 1 is a 2-week cycle and consists of 2 visits, the dosing visit (W0) and a visit 24 hours after dosing (W0D2).

#### Week 0 day 1 (W0)

For the first patients included in the phase IIa part, IPH2201 and ibrutinib will be administered as combined therapy from W0 visit.

The following pre-dose assessments must be done prior to IPH2201 administration:

- Inclusion/Exclusion criteria
- Concomitant illness/Concomitant medication
- Safety assessments
  - o Vital signs (including weight)
  - o Physical examination, focused on symptoms and new findings (from screening visit)
  - ECOG status
  - Adverse events
  - o 12-lead ECG
- Pre-dose Safety laboratory (H0)

Release date: Edition number 12 August 2016 MOD-3783

GED version

- o Hematology: red blood cell(s) (RBC), WBC with differential count, platelets, hemoglobin; Mean Corpuscular Volume (MCV), hematocrit
- Biochemistry: sodium, potassium, chloride, bicarbonate, calcium, magnesium, phosphate, total proteins, and albumin, urea, uric acid, creatinine, calculated creatinine clearance, ALP, total bilirubin, LDH, AST (SGOT), ALT (SGPT), GGT, amylase, lipase, glucose, CRP and fibrinogen
- Pregnancy test
- Pre-dose PK/PD assessments (H0)

IPH2201 will be administered as a 1-hour intravenous (IV) infusion. Patients will be treated at the recommended dose by the Safety Committee.

H0 is the start time of the 1-hour infusion.

For patients in the phase IIa part, ibrutinib will be administered at the dose of 420 mg (three 140 mg capsules) orally once daily, from W0.

IP2201 will be administered first, immediately followed by ibrutinib.

The following post-dose assessments are required at W0:

- o 12-lead ECG at H0+3 +/- 1 hour
- Biochemistry at H0+4: sodium, potassium, chloride, bicarbonate, calcium, magnesium, phosphate, total proteins, and albumin, urea, uric acid, creatinine, calculated creatinine clearance, ALP, total bilirubin, LDH, AST (SGOT), ALT (SGPT), gamma glutamyl transferase (GGT), amylase, lipase, glucose, C-reactive protein (CRP) and fibrinogen
- Hematology at H0+4: RBC, WBC with differential count, platelets, hemoglobin; MCV, hematocrit
- o PK assessments at H0+1 (end of IPH2201 infusion)

### Week 0 day 2 (W0D2)

To be performed 24 hours +/- 6 hours after the administration visit at W0. The evaluations and sampling quoted at this visit are to be performed.

- Concomitant illness/Concomitant medication
- Vital signs
- Adverse events
- Hematology
- o Biochemistry
- o RSA
- o NK & T cells markers and Immunophenotyping
- Functional assay (PBMC)

Release date: Edition number

GED version

# 6.2.2.2 Cycle 2

Cycle 2 is a 2-week cycle and consists of 2 visits, the dosing visit (W2) and a visit 24 hours after dosing (W2D2).

### Week 2 day 1 (W2)

The following pre-dose assessments must be done prior to IPH2201 and ibrutinib administration:

- Concomitant illness/Concomitant medication
- Safety assessments
  - Vital signs (including weight)
  - Physical examination, focused on symptoms and new findings (from screening visit)
  - o ECOG status
  - o Adverse events
- Pre-dose Safety laboratory (H0)
  - Hematology
  - o Biochemistry
  - o Urinalysis
- Pre-dose PK/PD assessments (H0)
  - o PK

IPH2201 administration should be performed 14 days  $\pm$  3 days after previous administration. Redosing criteria include the resolution of any grade 3 or higher adverse event to grade 2 or lower, the absence of disease progression and the absence of grade 4 treatment-related non-hematologic AE following the previous administration.

The following post-dose assessments are required at W2 visit:

- PK assessments at H0+1 (end of IPH2201 infusion)
  - Biochemistry at H0+4: sodium, potassium, chloride, bicarbonate, calcium, magnesium, phosphate, total proteins, and albumin, urea, uric acid, creatinine, ALP, total bilirubin, LDH, AST (SGOT), ALT (SGPT), gamma glutamyl transferase (GGT), amylase, lipase, glucose, C-reactive protein (CRP) and fibrinogen
  - Hematology at H0+4: RBC, WBC with differential count, platelets, hemoglobin; MCV, hematocrit

### Week 2 day 2 (W2D2)

To be performed 24 hours  $\pm$  6 hours after the administration visit at W2. The following evaluations should be performed at the visit:

- o Concomitant illness/Concomitant medication
- Vital signs
- o Adverse events
- Hematology
- o Biochemistry

Release date: Edition number 12 August 2016 MOD-3783

GED version

# 6.2.2.3 Cycle 3

Cycle 3 is a 2-week cycle and consists of 1 dosing visit (W4) only.

### Week 4 day 1 (W4)

The following pre-dose assessments must be done prior to IPH2201 and ibrutinib administrations:

- Concomitant illness/Concomitant medication
  - Safety assessments
    - Vital signs (including weight)
    - o Physical examination, focused on symptoms and new findings (from screening visit)
    - ECOG status
    - Adverse events
  - Pre-dose Safety laboratory (H0)
    - o Hematology
    - o Biochemistry
    - o Coagulation factors
  - Other specific assessments are required at W4 visit
    - Tumor assessment: A tumor assessment by physical examination and a new CT-scan are required at W4 visit

IPH2201 administration should be performed 14 days + 3 days after previous administration IP2201 will be administered first, followed by ibrutinib, to be taken after the end of IPH2201 perfusion.

There are no required post-dose assessments at W4

# 6.2.2.4 Cycle 4

Cycle 4 is a 2-week cycle and consists of 1 dosing visit (W6) only.

#### Week 6 day 1 (W6)

The following pre-dose assessments must be done prior to IPH2201 and ibrutinib administrations:

- Concomitant illness / Concomitant medication
- Safety assessments as following:
  - o Vital signs (including weight)
  - Physical examination, focused on symptoms and new findings (from screening visit)
  - o ECOG status
  - Adverse events
- Pre-dose Safety laboratory (H0)
  - o Biochemistry
  - o Hematology
  - o A 12-lead ECG
- Pre-dose PK/PD assessments (H0)
  - o PK
  - 0

IPH2201 administration should be performed 14 days +/- 3 days after the previous administration.

Release date: Edition number 12 August 2016 MOD-3783

GED version

IP2201 will be administered first, followed by ibrutinib, to be taken after the end of IPH2201 perfusion.

- The following post-dose assessments are required at W6 visit:
  - PK assessments at H0+1 (at end of the 1-hour infusion of IPH2201)

### 6.2.2.5 Cycle 5 to cycle 15

From cycle 5 (W8) cycles last for 4 weeks and consist of 1 dosing visit only.

The following pre-dose assessments should be done prior to IPH2201 and ibrutinib administrations:

- Concomitant illness/Concomitant medication
- Tumor assessment:
  - a tumor assessment by physical examination is required at all dosing visits starting from W8 visit (monthly assessments);
  - a CT-scan should be performed at W16 and at any other visit to confirm a CR or progression, whenever one of these events is suspected
- Safety assessments
  - Vital signs (including weight)
  - o Physical examination, focused on symptoms and new findings (from screening visit)
  - o ECOG status
  - Adverse events
  - A 12-lead ECG is required at W16 and W32
- Pre-dose Safety laboratory (H0)
  - Hematology: RBC, WBC with differential count, platelets, hemoglobin; MCV and hematocrit
  - Biochemistry: sodium, potassium, chloride, bicarbonate, calcium, magnesium, phosphate, total proteins, and albumin, urea, uric acid, creatinine, calculated creatinine clearance, ALP, total bilirubin, LDH, AST (SGOT), ALT (SGPT), GGT, amylase, lipase, glucose, CRP and fibrinogen, required at W16, W24, W32, W40 and W48
  - o Urinalysis at predose of W32
- Pre-dose PK/PD assessments (H0)
  - o Pharmacokinetics at W12, W20, W28, W36 and W44

- Testing for IgG, IgM, IgA and total immunoglobulin levels in predose of W16 and W32
- Other specific assessments (H0)

IPH2201 administration should be performed 28 days +/- 7 days after the previous administration. IP2201 will be administered first, followed by ibrutinib, to be taken after the end of IPH2201 perfusion. The following post-dose assessments are required:

- PK assessments at H0+1 (end of IPH2201 infusion) at W12, W20, W28, W36 and W44

Release date: Edition number

GED version

[figure not shown]

# 6.3 END OF TREATMENT VISIT

The end of Treatment (EOT) visit takes place in case of premature discontinuation or  $14 \pm 5$  days after last treatment cycle.

The following assessments are required:

- Concomitant illness/Concomitant medication
- Tumor assessment:
  - o a tumor assessment by physical examination
  - a CT-scan should be performed to confirm a CR or progression, whenever one of these events is suspected
- -
- Safety assessments:
  - Vital signs (including weight)
  - o Physical examination, focused on symptoms and new findings (from screening visit)
  - ECOG status
  - Adverse events
- Safety laboratory
  - o Hematology
  - o Biochemistry
  - o Coagulation factors
  - o Urinalysis
- PK/PD assessments

 Serum Ig: Testing for IgG, IgM, IgA and total Immunoglobulin levels are required at EOT visit

### 6.4 FOLLOW-UP VISITS

# Phase lb:

For the patients included in phase Ib, follow-up visits are performed after the End of Treatment visit and during a 12-month period. The follow-up visits FU1 to FU4 will be done monthly, follow-up visit FU5 will take place 2 months after FU4, and follow-up visits FU6 and FU7 will be performed every 3 months

### Phase IIa:

For the patients included in the phase IIa part of the study, follow-up visits are performed after the End of Treatment visit every 3 months for a 12-month period.

At follow-up visits the following assessments are required:

- Concomitant illness/Concomitant medication
- Tumor assessment:
  - o a tumor assessment by physical examination is required at all follow-up visits

Release date: Edition number

MOD-3783

12 August 2016

GED version

- a CT-scan should be performed to confirm a CR or progression, whenever one of these events is suspected
- Safety assessments:
  - Vital signs (including weight)
  - o Physical examination, focused on symptoms and new findings (from screening visit)
  - ECOG status
  - o Adverse events
- Safety laboratory
  - o Hematology
  - Biochemistry: at FU3, FU5, FU6, FU7 in phase lb, and at FU1, FU2, FU3 and FU4 in phase II (assessments every 3 months)
- PK/PD assessments

  o Pharmacokinetics

### 6.5 END OF STUDY VISIT

The End of Study (EOS) Visit is performed in case of premature discontinuation or at the end of the follow-up period.

The following assessments are required:

- Concomitant illness/Concomitant medication
- Tumor assessment:
  - o a tumor assessment by physical examination is required
  - a CT-scan should be performed to confirm a CR or progression, whenever one of these events is suspected
- Safety assessments:
  - o Vital signs (including weight)
  - Physical examination, focused on symptoms and new findings (from screening visit)
  - o ECOG status
  - o Adverse events
  - 12-lead ECG at EOS
- Safety laboratory
  - o Hematology
  - Biochemistry
  - Thyroid gland
  - o Pregnancy test : urinary test
- PK/PD assessments

Release date: Edition number

GFD version

# 7 Efficacy Parameters

The primary objective of the phase IIa is to evaluate the anti-leukemic activity of the combination of IPH2201 and ibrutinib in patients with relapsed or refractory CLL previously treated with at least one line of treatment.

### 7.1 COMPLETE REMISSION, DEFINITION

A CR is defined in the IWCLL guidelines (Hallek, Cheson et al. 2008). CR requires all the following criteria assessed at least 2 months after the discontinuation of IPH2201:

- Peripheral blood lymphocytes <4x10^9/l (4 000 /μl)
- o Absence of significant lymphadenopathy by physical examination, with lymph nodes ≤ 1.5 cm in diameter
- o Absence of constitutional symptoms
- o Blood counts above the following values
  - Neutrophils >1.5x10^9/l without need for exogenous growth factors
  - Platelet >100x10^9/l (100 000/µl) without need for exogenous growth factor
  - Hemoglobin >11g/dl without red blood cell transfusion or ned for exogenous erythropoietin

Several examinations should be performed in this clinical trial to confirm the CR

- CT scans of abdomen, pelvis and thorax should be performed to confirm the absence of significant lymphadenopathy, hepatomegaly and splenomegaly.
- o Bone marrow examination (with aspiration and biopsy) performed at least 2 months after the achievement of CR criteria, clinically and in peripheral blood. To define a CR, the marrow sample must be at least normocellular for age with less than 30% of nucleated cells being lymphocytes. Lymphoid nodules should be absent. In some cases, lymphoid nodules can be found; the nodules should be recorded as "nodular PR". Immunohistochemistry should be performed to define whenever these nodules are composed primarily of T cells or lymphocytes other than CLL cells or of CLL cells, reflecting residual disease

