### PHASE II flow chart foot notes:

- 1 IPH2201 administration should be performed 14 days +/- 3 days after previous administration from W2 to W6. Starting from W8, IPH2201 administration should be performed 28 days +/- 3 days after previous administration.
- 2 Ibrutinib will be administered at the dose of 420 mg (three 140 mg capsules) orally once daily.
- 3 Screening visit must be performed 3 weeks maximum prior to W0;
- 4 Full physical exam at baseline; focused on symptoms and any new findings at all subsequent visits
- 5 Hematology: red blood cell(s) (RBC), WBC with differential count, platelets, hemoglobin; mean Corpuscular Volume (MCV), hematocrit. At W0 H0+4 and W2 H0+4, additional samplings are required
- Biochemistry: sodium, potassium, chloride, bicarbonate, calcium, magnesium, phosphate, total proteins, and albumin, urea, uric acid, creatinine, calculated creatinine clearance, ALP, total bilirubin, LDH, AST (SGOT), ALT (SGPT), gamma glutamyl transferase (GGT), amylase, lipase, glucose, C-reactive protein (CRP) and fibrinogen. At every visit from screening until W6 visit, then every 2 months, at W16, W24, W32, W40, W48 visits; at EOT, FU1 to FU4 and EOS. At W0 H0+4, additional samplings are required
- 7 Thyroid: TSH, Free T3 and Free T4
- 8 Coagulation factors: activated partial thromboplastin time (APTT), prothrombin time (PT). at Screening, at predose of W4 visit and at EOT
- 9 EOT visit To be performed in case of premature discontinuation or 28 days +/-3 days after W48 visit
- 10 Urinalysis: PH, Glucose, Leucocytes, proteins, blood and hemoglobin, to be performed at screening, in predose of W2 and W32 and at EOT
- 11 12-lead ECG should be performed at screening, W0 predose, W0 H0+3 +/- 1 hour, in predose of W6, W16, W32 visits and at EOS
- 12 End of study visit to be performed in case of premature discontinuation, or at the end of the follow up, +/- 7 days after previous visit
- 13 Testing for IgG, IgM, IgA and total immunoglobulin levels at screening, in predose of W16, W32 visits and at EOT

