- 14 Tumor Assessment: pretreatment tumor assessment should be performed within 3 weeks before the first dose. Tumor assessments by physical examination should be performed at W4, W8; afterwards at all visits until EOS. A CT scan (with contrast unless contraindicated) of the chest, abdomen, and pelvis is required for the pretreatment tumor assessment. New CT-scan should be performed at W4, and thereafter at W16 and at EOS, and to confirm any CR or progression.
- 15 Follow up visits: to be performed every 3 months after EOT and during 12 months
- 16
  17 For patients in Phase 2a part, PK assessments at W0 H0 (pre-dose) and H0+1 (end of IPH2201 infusion); W0D1, W6, W12, W20, W28, W36, W44, W52 at H0 and H0+1; EOT, FU1 to FU4 (every 3 months); EOS

A bone marrow examination is required at screening if not performed within 1 month; at least 2 months after the achievement of complete response (CR) criteria clinically and in peripheral blood, in order to confirm the CR; and in the event of disease progression.

Release date: Edition number

MOD-3783

12 August 2016

GED version

Correlation tables of visit names between Protocol V4.0 and Protocol V5.0 for patients enrolled according to previous versions of protocol

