# 3 STUDY DESIGN

### 3.1 STUDY ENDPOINTS

# 3.1.1 Primary Endpoints

Part 1: phase lb

The primary endpoint will be the safety of 2 repeated administrations of IPH2201 given as a single agent during 4 weeks and, thereafter, given in combination with ibrutinib during 52 weeks:

- Occurrence of DLT and identification, if any, of the MTD, during the administration of IPH2201 as a single agent and given in combination with ibrutinib
- Occurrence of AEs and SAEs

Safety will be assessed using the CTCAE version 4.03, apart from neutropenia and thrombocytopenia which severity will be graded by using the IWCLL grading scale reported in appendix IV. It will include a descriptive analysis of the frequency and severity of AEs, as well as clinical laboratory tests collected to assess lab abnormalities, results of vital sign measurements, electrocardiograms (ECGs), physical examinations and imaging studies. Related AEs will be followed to resolution (≤ grade 1) unless deemed irreversible.

Part 2: phase IIa

The primary endpoint will be the rate of complete response, achieved with a combination of IPH2201 and ibrutinib, assessed 52 weeks after the beginning of the treatment, defined according to the guidelines of IWCLL (Hallek, Cheson et al. 2008), and confirmed by a bone marrow biopsy.

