### 3.4 DURATION OF STUDY

The recruitment of up to 45 patients is expected to approximately cover an 18-month period.

Patients in part 1 may be treated up to 56 weeks: 4 cycles of 2 weeks each followed by 12 cycles of 4 weeks each.

Patients in part 2 may be treated up to 52 weeks: 4 cycles of 2 weeks each followed by 11 cycles of 4 weeks each.

Treatment by ibrutinib will be at least administered until the end of the study follow-up unless a disease progression (IWCLL), untoward toxicity or consent withdrawal leads to the premature interruption of the treatment.

Patients will be followed for 12 months after interruption of IPH2201 treatment (End of Study visit). Furthermore, patients will be enrolled in a post study follow-up enabling the documentation of disease progression (IWCLL) or death for 3 additional years after the completion of their study follow-up.

CONFIDENTIAL

Release date: Edition number

GED version

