8.1 Rate of complete remission

In both phases, the rate of complete remission is assessed 52 weeks after the initiation of combined treatment

The rate of complete remission (CR) will be calculated in the main endpoint population (see §4.2.2). Within this population, the CR rate will be computed as the number of patients with a confirmed complete remission at W52 divided by the total number of patients in the main endpoint population.

The rate of complete remission with 95% confidence interval will be summarized overall and in the subgroup treated at the RP2D.

In order to claim a CR, the CR must be confirmed. In order to have a confirmed CR (cCR), the CR must be confirmed by a scan and a bone marrow assessment assessed at least 2 months after the first occurrence of CR.

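### Protocol 7.1 dates complete response from 2 months after IPH2201 stops, so on the planned schedule a phase IIa treatment completer cannot be a CR at the 52-week primary reading; SAP 8.1 uses a different clock, and the protocol's 4/27 rule a different end point in time

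*Protocol*

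**What the plan says.** **Definition of CR.** Protocol 7.1 opens with "CR requires all the following criteria assessed at least 2 months after the discontinuation of IPH2201". The lymphocyte, node, symptom and blood-count criteria follow under that clause. The marrow requirement in the same section, like the flow-chart notes, has another starting point: "at least 2 months after the achievement of complete response (CR) criteria clinically and in peripheral blood, in order to confirm the CR". Appendix III tabulates the CR criteria with no interval after stopping treatment.

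**Time of the primary reading.** Protocol 3.1.1 has phase IIa CR "assessed 52 weeks after the beginning of the treatment, defined according to the guidelines of IWCLL". SAP 8.1 says "In both phases, the rate of complete remission is assessed 52 weeks after the initiation of combined treatment" and sets the numerator as "the number of patients with a confirmed complete remission at W52 divided by the total number of patients in the main endpoint population". It requires confirmation by scan and marrow at least 2 months after CR first occurs, and it mentions no off-IPH2201 interval.

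**Schedule.** Protocol 3.4: "Patients in part 2 may be treated up to 52 weeks". Phase II flow-chart note 9: "EOT visit To be performed in case of premature discontinuation or 28 days +/-3 days after W48 visit". Note 15: "Follow up visits: to be performed every 3 months after EOT and during 12 months".

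**Early stopping of IPH2201.** The protocol synopsis (Follow-up period), protocol 3.3 and SAP 3.2.3 provide for shorter IPH2201 treatment when a CR with undetectable MRD has been documented over 2 months. That presupposes a CR recorded on treatment.

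**Decision rule.** The protocol synopsis (Statistical methods) and protocol 10.2 call for further investigation if at least 4 of 27 patients reach CR, counted to study end. SAP 3.3.2 gives the same threshold with no time.

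**The concern.** The primary endpoint needs one definition of CR and one reading time, and the documents give two of each. If the opening clause of 7.1 is applied as written, a patient who takes all planned IPH2201 cannot be a CR at 52 weeks, whatever the treatment does. That CR could enter only the secondary endpoint of CR during follow-up. Under the SAP 8.1 clock the same patient can be a primary CR. With a threshold of 4 events, the choice of text can decide whether the trial is positive.

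The end-of-study wording of the 4/27 rule is a separate fault. The protocol's own background (1.1.5.1) shows CR on ibrutinib alone rising with time, so a 5% null has meaning only at the time point at which CRs are counted.

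**Working it through.** **1. The planned rule.** Inputs (protocol 10.2, SAP 3.3.2): n = 27, positive if at least 4 CRs, p0 = 0.05, p1 = 0.20, one-sided alpha 0.05, power 0.80.

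P(X ≥ 4) = 1 − Σ(k = 0 to 3) C(27,k) p^k (1−p)^(27−k)

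- p = 0.05: 0.0437
- p = 0.20: 0.8177

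The design reproduces, and 27 is the smallest n that meets both limits exactly. The sample size is not in error.

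**2. The calendar under literal 7.1.** Take 2 months as 56 to 62 days (8 to 8.9 weeks).

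- Last planned phase IIa dose W48; reading W52. Days since last dose: 28, or 31 at the edge of the visit window. Required: 56 to 62.
- Earliest time that meets 7.1: 48 + 8 = W56 to 48 + 8.9 = W56.9. Counted from the end of the 52-week treatment period: W60 to W60.9.
- First scheduled visit after that: 3 months (13 weeks) after W52, about W65.
- Protocol 6.3 dates the end-of-treatment visit 14 ± 5 days after the last cycle. Even counted from the end of a 28-day cycle, that is at most 28 + 19 = 47 days after the last dose, still under 56.
- To qualify at W52, the last dose must fall by 52 − 8 = W44, or 52 − 8.7 = W43.3 with average calendar months.
- Pooled phase Ib patients: ibrutinib starts at W4, so 52 weeks of combination ends at W56. Last dose W52, earliest W60 to W60.9: the same gap.

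Exception: protocol 6.2 and 6.2.2.5 allow ±7 days between 4-weekly doses, counted from the previous dose. Five intervals each shortened by 7 days bring the last dose to 48 − 5 = W43, which is 9 weeks before a calendar W52. This is permitted but is not the planned schedule.

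**3. Effect on the decision rule.** Let d be the share of true CR patients whose IPH2201 stopped early enough to satisfy 7.1 at W52. The documents do not give d. The countable rate at a true 20% is 0.20 × d.

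| d | countable rate | P(at least 4 of 27) |
|---|---|---|
| 0 (all complete) | 0 | 0 |
| 25% | 0.05 | 0.0437 |
| 50% | 0.10 | 0.2821 |
| 75% | 0.15 | 0.5928 |
| 100% | 0.20 | 0.8177 |

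**4. End-of-study counting with no added IPH2201 effect.** End of study is about month 24 (52 weeks of treatment plus 12 months). Protocol 1.1.5.1 gives CR rates at 12 and 42 months; interpolate linearly (an assumption).

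- Untreated: 6 + (23 − 6) × 12/30 = 12.8%. P(at least 4 of 27) = 0.4605.
- Previously treated: 3 + (7 − 3) × 12/30 = 4.6%. P = 0.0337. The protocol labels these figures relapses; they are read here as CR.
- Randomized trial in untreated patients, 4% at a median of 18 months: P = 0.0215.

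**The case against.** The strongest reply is that the clause in 7.1 stands alone and will not drive the analysis. Protocol 10.1 leaves analytical detail to the SAP, and SAP 8.1 has no off-treatment condition. The visit schedules call for CT at any dosing visit to confirm a suspected CR. The early-stop passages need a CR on treatment, and Appendix III lists the criteria without this interval. The primary endpoint cites the IWCLL guideline, not section 7.1. All of that stands, and it makes the SAP reading the likely one. It does not remove the conflict. SAP 8.1 gives a confirmation rule but no list of CR criteria, nothing in the SAP withdraws the 7.1 condition, and sites assess response under the protocol.

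A reader might go further in four ways that the documents do not support.

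- *The trial cannot succeed.* Zero follows only if 7.1 is applied literally and every patient completes on the nominal schedule. Patients who stop early can qualify, and so can the dosing-window corner case.
- *The SAP introduced a new clock.* It did not. Its clock is already in the protocol's marrow requirement and flow-chart notes, so the protocol also conflicts with itself.
- *The false-positive risk is 46%.* That needs an all-untreated sample and an end-of-study count. Relapsed and refractory patients are also eligible, and the treated figures give about 3.4%, below the planned 4.4%.
- *Requiring confirmation by W52 costs power.* It would exclude a CR first met after about W43 to W44, but there is no power loss if the planned 20% already means confirmed CR, and SAP 8.1 says a CR must be confirmed to be claimed.

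Whether the off-treatment interval belongs to the cited guideline cannot be settled from these documents.

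**Conclusion.** The plan is wrong as written and should be corrected before the primary analysis. On the nominal schedule, literal 7.1 and the 52-week endpoint cannot both hold for a treatment completer. The shortfall at W52 is 4 to 4.9 weeks counted from the last dose. The consequence ranges from none (alpha 4.4%, power 81.8%) if SAP 8.1 is followed, to a CR count of 0 if 7.1 is followed and all 27 complete. The values in between depend wholly on the assumed share d.

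The undated or end-of-study 4/27 rule is a second, smaller fault. With no added effect, the chance of a positive result at month 24 runs from about 2% to 46%, depending on prior treatment and on the interpolation.

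**What to change.** 1. In protocol 7.1, 3.1.1 and 10.2 and SAP 8.1, state one clock for the primary endpoint: the 52-week CR is the SAP 8.1 confirmed CR, with 2 months counted from first meeting CR criteria. Say that the post-discontinuation condition in 7.1 does not govern this reading. A post-discontinuation CR can be reported under the existing secondary endpoint of CR during follow-up (protocol 3.1.2, SAP 3.1.2.2).
2. In the protocol synopsis and 10.2, replace the end-of-study count in the 4/27 rule with the 52-week reading, and add that time to SAP 3.3.2.
3. In SAP 8.1, state that the reading is 52 weeks from the start of the combination (W52 in phase IIa, W56 for pooled phase Ib patients), and whether a confirmation dated after that visit counts.
4. Reconcile 7.1, Appendix III and SAP 8.1 with the early-stop passages (protocol synopsis and 3.3, SAP 3.2.3). Reconcile also the end-of-treatment dates: W56 in the phase I flow-chart heading, 14 days after W52 in its note 9, 28 days after W48 in phase II note 9, and 14 ± 5 days after the last cycle in protocol 6.3. Which stopping rule or visit date is right is not a question for this review.

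The cost is wording only. The sample size and the threshold of 4 do not change.
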